4. OBJECTIVES AND RESEARCH QUESTIONS

Study objectives and research questions are listed in the Table 2.

Table 2 Objectives and Research Questions

Objectives	Research Questions
Primary Objective To assess the effectiveness among overall and sub-group Chinese CHB patients who receive TDF treatment in real-world	Among the overall analysis population and relevant sub-group* populations: • Proportion of patients who achieve complete virologic response (CVR) at
	 weeks of 48, 96, and 144. Proportion of patients who achieve HBeAg loss and/or HBeAg. seroconversion in HBeAg positive patients at weeks of 48, 96 and 144.
	 Proportion of patients who achieve HBsAg loss and/or HBsAg seroconversion at weeks of 48, 96 and 144.
	 Proportion of patients who achieve transaminase normalization at weeks of 48, 96 and 144.
	 Time to CVR, defined as time from baseline to the first occurrence of CVR (if applicable)
Secondary Objective	
To assess the renal function change among overall and sub-group CHB patients during TDF	Among the overall analysis population and relevant sub-group* populations:
treatment	 Proportion of patients whose eGFR decline >20% from baseline at weeks of 48, 96,

Objectives	Research Questions
	and 144.
	 Percentage of change from baseline in eGFR at weeks of 48, 96, and 144
	Change from baseline in eGFR values at weeks of 48, 98 and 144
	 Proportion of patients with confirmed serum phosphate Grade 3 or 4 abnormality (<2.0 mg/dL) at weeks of 48, 98 and 144.
	 The percentage of change from baseline in serum phosphate at weeks of 48, 98 and 144.
	 Change from baseline in phosphorus values at weeks of 48, 98 and 144
Exploratory Objectives	
To explore the Bone Mineral Density (BMD) change among overall and sub-group CHB patients during TDF treatment	Percentage of BMD change from baseline at weeks of 48, 96, and 144
To investigate predictors of effectiveness among CHB patients who receive long-term	Baseline or on-treatment predictors (e.g. baseline characteristics, etc).
TDF treatment	Treatment effectiveness, including CVR, HBeAg loss and/or HBeAg, transaminage normalization
To explore risk factors of safety among CHB patients who receive long-term TDF treatment	Baseline or on-treatment risk factors (e.g. baseline characteristics, co-morbidities, and concomitant treatment etc).
	Renal impairment, including eGFR decline and serum phosphate
	Bone impairment, including BMD decline

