6.1. Inclusion Criteria

Participants will be eligible to be included in this study only if all of the following criteria apply:

- 1. Male or female participants aged 12 years and above, at the time of signing the informed consent.
- 2. Participants who are diagnosed with CHB and meet the criterion of antiviral treatment for HBV infection judged by certified physicians.
- 3. Participants who newly initiate TDF ((only including brand TDF, Viread, and generic TDF, Beixin and Naxinde, which passed China generic quality consistency evaluation by Apr. 1 2018) monotherapy or combination therapy for the treatment of CHB by the judge of investigators at the study entry.
- 4. Participants who have already started TDF at the entry of study and will continue to be treated TDF (including brand TDF, Viread, and generic TDF, Beixin and Naxinde which passed China generic quality consistency evaluation by Apr. 01 2018) with essential medical information record and lab test reports available at the initiation of TDF treatment and follow-up visit.

Essential medical information record and lab test reports:

• *At the initiation of TDF treatment:*

- i. TDF treatment detail: TDF dose, brand name, start date;
- ii. Lab test (within +/-4 weeks of TDF treatment initiation): HBV DNA quantification (using high sensitive real-time PCR assays for HBV DNA quantification with lower limit of detection of 20IU/ml), ALT and/or AST, Serum creatinine and Serum phosphate, HBsAg/Anti-HBs and HBeAg/Anti-HBe
- iii. Medical information: CHB diagnosis and treatment history, co-morbidity, concomitant treatment
- The following visits under TDF treatment prior to entry of the study (At least once following visit record if TDF treatment >6 months):
 - i. Lab test: HBV DNA quantification (using high sensitive real-time PCR assays for HBV DNA quantification with lower limit of detection of 20IU/ml), Serum creatinine and Serum phosphate
 - ii. Medical information: co-morbidity, concomitant treatment, TDF treatment information

The proportion of patients who have already started TDF at the study entry will be monitored closely during study recruitment and will be kept less than 10% of the total study population.

- 5. Participants who are able to perform normal activities and seek regular medical care, e.g., willing to regularly perform lab test to monitor the treatment response.

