All the lab test and procedures in the SoA will be performed based on the judgement of investigators/treating physicians and patients' willingness as in real-world practice. To achieve consistent evaluation of the effectiveness and safety of TDF treatment, the minimal essential lab test requested by CHB management guideline, including HBV DNA, eGFR and serum phosphate, will be performed in central lab during patients'

routine clinical visits. Other lab tests and procedures will be performed in local hospitals where patients seek care. Results will be collected by the innovative electronic approach.

CONFIDENTIAL

Supplementary central lab operation information would be provided in the accompanying study procedure manual (SPM). The SPM will provide the site personnel with administrative and detailed information on how to minimize the impact of the introduction of central lab to routine practice.

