7.2. Baseline Data Collection

Baseline information collected (assessment values and date of assessment) includes:

- Socio-demographic information, e.g. age, sex, economic status, medical insurance coverage
- Health behaviour information, e.g. smoking status, alcohol consumption, health care seeking behaviour
- Physical examinations, e.g. weight, height
- Medical information, e.g. medical history, anti-Hep B diagnosis and treatment history, NUC drug resistance history, co-morbidity, concomitant treatment, decompensated cirrhosis/liver disease and related complications
- TDF treatment details, e.g. TDF dose, brand name, start date
- Initial tests when initiating TDF therapy, including
 - HBV serology
 - o HBV DNA
 - o Serum creatinine and eGFR [MDRD equation]
 - Serum phosphate
 - o Alanine transaminase (ALT) and aspartate transaminase (AST)
- Other tests and procedures collected if available
 - o AFP

- Hepatic ultrasound
- o Genotype
- o Bone mineral density
- o Liver biopsy
- o Transient elastography (fibrotouch or fibroscan)
- Hepatic ultrasound/ computed tomography (CT) /magnetic resonance imaging (MRI)
- Spontaneous AEs if available

To evaluate renal function, the estimated glomerular filtration rate (eGFR) will be calculated using the modification of Diet in Renal Disease (MDRD) equation:

Where the unit of creatinine is ml/min/1.73m². Baseline data will be collected using a specifically designed survey. For patients who initiate TDF treatment at the entry of the study, baseline information can be completed from investigator interviewing the patient.

For patients who have already been on TDF treatment at the study entry, their previous data related to initiation of TDF treatment and follow-up will be collected from (electronic) medical records as needed if available.

Three essential lab tests, HBV DNA, serum creatinine, and serum phosphate, will be performed in a central lab. Patients' other data will be collected using electronic approaches, mainly from lab test reports or medical records at baseline and follow-ups.

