9. STATISTICAL CONSIDERATIONS

9.1. Sample Size Determination

9.1.1. Hypotheses

No formal hypotheses will be tested, as this will be a descriptive study. The objective of this study is to observe the effectiveness and safety among Chinese CHB patients who receive long-term TDF treatment in real-world setting.

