9.1.2. Sample Size Assumptions

Sample sizes are estimated based on feasibility and precision level achieved as no formal hypothesis will be tested in this study.

The primary objective of this study is to assess the effectiveness of TDF, with one important indicator being the proportion of subjects who achieve the CVR (i.e. HBV-DNA undetectable) at weeks of 48, 96, and 144. To be able to assess the CVR achievement at week 144, a sample size of 2,000 patients will provide a precision of no more than 2.2%, assuming the percentage of patients achieving CVR is 80% and the rate of loss-to-follow-up and discontinuation is 35%. The precision is calculated by the following: precision = $Z_{(1\alpha/2)}$ *SQRT(p*(1-p)/N), where Z is the critical value of normal distribution corresponding to the probability of 1- α /2 (corresponding to (1- α)*100% confidence interval), and p is the percentage of patients achieving CVR. It is half of the width of 95% confidence interval for the point estimate, which means that the lower and upper bounds of the 95% confidence interval for the patient proportion of interest will be within 2.2% of the point estimate (point estimate +/- 2.2%). In addition, there will be approximately a 73% probability of identifying a least one AE with a true AE rate of 0.1%.

For an exploratory purpose, more calculations about the precisions of evaluating the CVR achievement percentage are also provided for difference sub-populations, such as HBeAg positive or Cirrhosis. Assuming HBeAg positive (Cirrhosis) is made of 54.5% (20%) of HBV patients, the percentage of patients achieving CVR is 80% and 3 -year drop-out rate is 35%, a sample size of N=2000 will have 1090 (400) patients in the interested group and about 708 (260) completers and a precision of no more than 0.029 (0.049) [You, 2016].

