9.3.4. Exploratory Analyses

9.3.4.1. Bone safety

Patients' BMD change from baseline during TDF treatment period will be explored.

• Percentage of BMD change at weeks of 48, 96, and 144 will be summarized using appropriate descriptive statistics for the overall analysis population and by subgroup populations.

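### The only bone measure named is raw percentage BMD change; with no comparator it carries expected age-related change, and a reported Z-score would be a cheap addition (minor)

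*Protocol*

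**What the plan says.** Table 2 in section 4 gives the bone research question as "Percentage of BMD change from baseline at weeks of 48, 96, and 144". Section 9.3.4.1, the only analysis text on bone, repeats it: "Percentage of BMD change at weeks of 48, 96, and 144 will be summarized using appropriate descriptive statistics for the overall analysis population". That sentence goes on to include subgroup populations, and both section 4 and section 9.3.2 list age and gender among the subgroup factors. Neither place names a Z-score, a T-score or any other referenced value.

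A separate exploratory objective in Table 2 looks for risk factors for safety and lists "Bone impairment, including BMD decline" as an outcome. Section 9.3.4 gives no method, scale or threshold for it.

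The setting matters too:
- Section 6.1 admits "Male or female participants aged 12 years and above, at the time of signing the informed consent" and sets no upper age.
- Section 7.3 follows patients for 3 years.
- Section 12 acknowledges that there is no comparison group and suggests a historical comparison.
- BMD sits under "Other tests and procedures collected if available" in section 7.2, and section 7 says of everything outside the central laboratory: "Other lab tests and procedures will be performed in local hospitals where patients seek care".
- Section 9.1.1 states: "No formal hypotheses will be tested, as this will be a descriptive study".

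**The concern.** BMD is expected to change over almost three years whether or not a patient takes TDF. It rises while a patient is growing and tends to fall in later adult life. Percentage change from baseline takes out the starting level but not that trend. With no untreated group and no age and sex reference, the reported figure is the sum of the expected change and anything else, including a drug effect.

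Two misreadings are then possible under a bone safety title. A fall in older patients may be taken as bone toxicity when it is no larger than expected for age. A rise in a growing patient may be taken as reassurance when it is smaller than expected.

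Section 9.3.3 makes the contrast visible: its models for change in eGFR and serum phosphate include age and gender as fixed effects. No such adjustment is named for bone.

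**Working it through.** **Figures in the plan.** The protocol states no expected BMD change, no number of scans and no share of adolescents, so there is no bone figure to reproduce. The relevant count is completers: 2000 × (1 − 0.35) = 1300, from section 9.1.2 and Table 3. With 80% responding, 1.96 × √(0.8 × 0.2 / 1300) = 0.0217, which matches the stated 2.2%. That precision is for virologic response and says nothing about BMD.

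**Follow-up in years.** Weeks × 7 / 365.25:
- week 48: 0.92
- week 96: 1.84
- week 144: 2.76

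On a linear scale, each 1% per year of expected change therefore contributes 0.92, 1.84 and 2.76 points to the percentage at the three time points.

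**Within a stratum (rates assumed).**
- Adults losing 0 to 1% per year: 0 to −2.76 points at week 144 with no drug effect.
- A growing patient expected to gain 5% per year: 5 × 2.76 = +13.8 points. If only half of that is achieved, the raw figure is +6.9 and still reads as a gain.

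Reporting by age group leaves both quantities in place, because each is the expected change inside the stratum.

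**Overall mean (all three inputs assumed).** Let f be the share still growing, g their gain and a the adult loss, both in % per year. The expected drug-free mean at week 144 is 2.76 × [f·g − (1 − f)·a].
- f = 0, a = 0.5 to 1: −1.38 to −2.76
- f = 1%, g = 1 to 5, a = 0: +0.03 to +0.14
- f = 10%, g = 1 to 5, a = 0: +0.28 to +1.38

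Across f = 0 to 10%, g = 1 to 5 and a = 0 to 1, the range is about −2.8 to +1.4 points.

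**How far adolescents alone can move the mean.** Compared with having none, the shift is f × (growth part + loss part). Take a deliberately high growth rate of 8% per year (8 × 2.76 = 22.08) and an adult loss of 1% per year (2.76), which sum to 24.84:
- f = 0.5%: 0.12 points
- f = 1%: 0.25 points
- f = 5%: 1.24 points

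These are upper bounds. They apply the fastest growth for the whole period, even to patients who enter at 16 or 17.

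**How many pairs there might be.** Those three shares of 1300 completers give 6.5, 13 and 65 under-18s. If paired BMD exists for an assumed 5% to 30% of completers:
- under-18 pairs: from 6.5 × 0.05 = 0.3 to 65 × 0.30 = 19.5
- adult pairs: from 0.95 × 1300 × 0.05 = 62 to 0.995 × 1300 × 0.30 = 388

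**The case against.** The best defence is that the protocol already does much of what is needed. The bone summary extends to subgroups, and age and gender are among them, so younger and older patients can be shown apart; only the age cut-off is open. Section 12 names the missing comparator as a major limitation. Section 9.3.5 leaves room for further exploratory analyses in the reporting and analysis plan, which is not at hand. The measure is exploratory and depends on scans done in routine care. A Z-score would not restore a causal reading, and reports from different hospitals may use different references.

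Most of this stands and sets the severity. It does not remove the point: strata still contain their own expected change, admitting that there is no comparator does not supply a reference, and the protocol itself names the measure in two places.

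Three stronger readings are tempting but not supported.
- A reader might infer that adolescents materially distort the overall figure. The protocol gives no adolescent share, and at shares of 0.5% to 1% even extreme rates move the mean by at most 0.12 to 0.25 points.
- A reader might infer that age will emerge as a spurious risk factor for bone impairment. That would need the risk-factor objective to use raw percentage change, and the protocol fixes no scale for it. Age as a descriptive correlate of BMD decline would also be a legitimate result.
- A reader might infer that the study claims a TDF effect on bone from this summary. Section 9.1.1 makes the study descriptive.

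**Conclusion.** The point holds as a minor one. Raw percentage BMD change, overall and by subgroup, is the only bone measure the protocol names. In a single treated cohort followed for 2.76 years, it cannot separate expected age-related change from anything else.

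The firm part of the size is arithmetic: 2.76 points at week 144 for each 1% per year of expected change. How many percent per year apply, how many under-18s enrol and how many patients have paired scans are all assumptions, so no actual bias can be quoted. The more relevant component is probably ageing in adults, since it does not depend on adolescent numbers; the under-18 stratum could be nearly empty. No primary or secondary result is affected. Percentage change is not wrong in itself and should stay; what is lacking is a referenced value beside it.

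**What to change.** In Table 2 and section 9.3.4.1:

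1. Keep percentage BMD change at weeks 48, 96 and 144.
2. Add change from baseline in age- and sex-referenced BMD Z-score wherever the routine report gives one. Use a pair only if both values come from the same site and the same reference.
3. Make Z-score change the main measure for any patients under 18.
4. State the number of paired values at each time point, for both measures.
5. Note that a Z-score removes only the expected age and sex trend. It does not isolate a TDF effect or stand in for a comparator.

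The cost is wording in two places and one more item to extract from BMD reports that are already collected when available. No new scan, visit or change in sample size is needed. The downside is fewer evaluable pairs, because some reports will lack a Z-score or change reference, and reference data that may differ between local hospitals. Stating the paired counts lets the reader see how much is lost.

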9.3.4.2. Risk factors/Predictors of TDF effectiveness

To explore risk factors or predictors (e.g. baseline characteristics, co-morbidities, and concomitant treatment etc.) for effectiveness:

• Treatment effectiveness, including CVR, HBeAg loss and/or HBeAg. Seroconversion, transaminase normalization

Fisher exact test will be performed for the comparisons of the above treatment effectiveness endpoints in sub-groups of interest.

If data permits, generalized linear mixed model will be used to analyze CVR, HBeAg loss and/or HBeAg Seroconversion, transaminase normalization. More details will be included in RAP.

Time to CVR will be analysed by Kaplan-Meier curve, log-rank test will be performed separately for risk factors or predictors of interest, and multivariate analysis by Cox regression model will be conducted if data is applicable.

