7.3. Follow Up Data Collection

Study participants will be followed up for 3 years or until they withdraw from the study. Follow-up information will be collected at 6-month intervals:

- Regular tests
 - o HBV serology
 - o HBV DNA
 - o Serum creatinine and eGFR [MDRD equation]
 - Serum phosphate
 - Alanine transaminase (ALT) and aspartate transaminase (AST)
- Other tests and procedures
 - o AFP
 - o Hepatic ultrasound
 - Genotype
 - o Bone mineral density

- Liver biopsy
- o Transient elastography (fibrotouch or fibroscan)
- Hepatic ultrasound /computed tomography (CT) /magnetic resonance imaging (MRI)
- Updated CHB treatment details, e.g. any change to regimen or dosage and reason for change
- Comorbidity and concomitant medication review
- Spontaneous AEs if available
- For treatment adherence, it will be evaluated by the treating physician according to the patients' care seeking care, e.g. whether take the medication as prescribed, have you ever discontinued your medications and for how long?
- For participants who discontinue TDF prematurely, duration of treatment and reasons for TDF discontinuation will be recorded, e.g. SAEs, non-SAEs, and insufficient effectiveness.

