8.2. Withdrawal from the Study

A participant may withdraw from the study at any time at his/her own request, or may be withdrawn at any time at the discretion of the investigator for safety, behavioral, compliance or administrative reasons. If the participant withdraws consent for disclosure of future information, the sponsor may retain and continue to use any data collected before such a withdrawal of consent.

In this real-world study, participants will be considered withdrawal from the study if any of the following events occurs within the 3-year study period:

Discontinuation of TDF (Viread, Beixin or Naxinde) for at least 28 days

Participation in clinical trials for any new drugs not limited to CHB-related ones during the 3-year study period

Study closed/terminated

Withdrew consent

The overall duration of TDF treatment and the reason for discontinuation of TDF treatment will be collected and the patient's adherence will be evaluated by the investigator a designed questionnaire.

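### Time to CVR is shown by Kaplan-Meier only; if TDF stops are censored, 1-KM describes response as if nobody stopped and is not the real-world share of treated patients reaching CVR

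*Protocol*

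**What the plan says.** Protocol section 4 (Table 2) lists time to CVR, measured from baseline to first CVR, among the research questions of the primary objective, with the qualifier that it applies where applicable. Its analysis appears only in section 9.3.4.2, an exploratory section on predictors: "Time to CVR will be analysed by Kaplan-Meier curve, log-rank test will be performed separately for risk factors or predictors of interest", followed by a Cox model if the data allow. No competing event is named and no censoring rule is given.

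Section 8.2 lists the events that count as study withdrawal. One is "Discontinuation of TDF (Viread, Beixin or Naxinde) for at least 28 days". Section 7.3 follows patients for three years or until withdrawal, and for those who stop early "reasons for TDF discontinuation will be recorded, e.g. SAEs, non-SAEs, and insufficient effectiveness".

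Section 9.1.2 makes one combined allowance: "the rate of loss-to-follow-up and discontinuation is 35" per cent. It does not say how much of this is stopping TDF and how much is loss to follow-up.

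Separately, section 9.3.2 estimates the proportion with CVR at weeks 48, 96 and 144, using tests within 28 days of each time point (3 months in supportive analyses).

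**The concern.** Once a patient has been off TDF for 28 days, the protocol ends follow-up. A later CVR is then neither on TDF nor observed. Under ordinary Kaplan-Meier use the patient is censored at that point, and the estimator lets the patients still on treatment stand in for the one who stopped. The curve then answers what response would be if nobody stopped. It does so validly only if stopping carries no information about future response, and stopping for insufficient effectiveness is directly related to response.

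Sections 5.1 and 5.4 describe a naturalistic study of outcomes in daily practice, where stopping is part of the outcome. A reader of the final report would easily take the height of a 1-KM curve at week 144 as the share of treated Chinese patients who reached CVR. That reading would be too favourable. The windowed proportions do not fill the gap, because they need a test inside the window and show status at one time, not cumulative response among everyone who was treated.

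**Working it through.** **The plan's own figure.** Section 9.1.2 states that "a sample size of 2,000 patients will provide a precision of no more than 2.2" per cent, "assuming the percentage of patients achieving CVR is 80% and the rate of loss-to-follow-up and discontinuation is 35" per cent. Check: 1.96 × sqrt(0.8 × 0.2 / (2000 × 0.65)) = 1.96 × sqrt(0.16 / 1300) = 0.0217, which rounds to 0.022. The figure reproduces. It concerns the week-144 proportion; the protocol gives no figure for time to CVR.

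**Model for the gap.** Assume constant, independent hazards: λ for first CVR and μ for stopping TDF. By week t:

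- With stops censored: 1-KM(t) = 1 − exp(−λt).
- With stopping as a competing event, the cumulative incidence is CIF(t) = λ/(λ+μ) × [1 − exp(−(λ+μ)t)].

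**Inputs.**

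- Stopping by week 144: 35% (all of the section 9.1.2 allowance), 17.5% (half) and 8.75% (a quarter). The shares are assumptions. μ = −ln(1 − d)/144 gives 0.002992, 0.001336 and 0.000636 per week.
- Speed of response: (a) 80% by week 144, λ = −ln(0.20)/144 = 0.011177. This reuses the 80% in section 9.1.2, which is a status at week 144, as a cumulative figure. (b) 76% by week 48, λ = −ln(0.24)/48 = 0.029732. (c) 93% by week 48, λ = −ln(0.07)/48 = 0.055401. Cases (b) and (c) are the HBeAg-positive and HBeAg-negative Phase III rates in section 3.2. Those rates use a 69 IU/mL threshold, so they are only a guide to speed.

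**Worked case, (a) with 35% stopping.** λ/(λ+μ) = 0.011177/0.014169 = 0.789. exp(−(λ+μ) × 144) = 0.20 × 0.65 = 0.13. CIF = 0.789 × 0.87 = 0.686. Gap = 80.0 − 68.6 = 11.4 points.

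**All cases at week 144** (gaps from unrounded values):

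| Response speed | 1-KM | CIF (gap), 8.75% stop | CIF (gap), 17.5% stop | CIF (gap), 35% stop |
|---|---|---|---|---|
| (a) 80% by week 144 | 80.0% | 77.3% (2.7) | 74.6% (5.4) | 68.6% (11.4) |
| (b) 76% by week 48 | 98.6% | 96.7% (1.9) | 94.6% (4.0) | 90.0% (8.6) |
| (c) 93% by week 48 | 100.0% | 98.8% (1.1) | 97.6% (2.3) | 94.9% (5.1) |

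Seven of the nine gaps exceed the 2.2 points for which the study was sized. Row (a) is a slow-response case: it implies only 1 − 0.2^(1/3) = 41.5% CVR at week 48, and slow response enlarges the gap.

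**Effect of visit timing.** These figures let CVR be seen when it occurs. A simulation in which CVR is detected only at 24-week visits, with all 35% as stops, gave larger gaps. For (a), 1-KM of 80% went with CIF of 66% under constant stopping, and 61% if 70% of stops fall in the first 48 weeks. For (b), 98.6% went with 86.5% and 79.6%. So 5 to 11 points is an upper bound on the share of stopping within the continuous-time model, not on every possible model.

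**The case against.** The strongest reply has four parts.

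- **Nothing says stops are censored or that 1-KM will be reported as a response rate.** This is correct. Patients who stop without CVR could be kept at risk to the end of follow-up as non-responders, which would come close to the cumulative incidence. Censoring rules are commonly left to the analysis plan, which is not shown. So a reader might infer that the protocol commits itself to an inflated response rate, and the text does not support that. What stands is narrower: the protocol fixes the method, its withdrawal rule leads to censoring under ordinary use, and the resulting curve has a restricted meaning that nothing in the protocol flags.
- **The section is about predictors, and those tests survive.** Also correct. With stops censored, log-rank and Cox compare cause-specific CVR hazards and remain usable. A reader might infer that subgroup comparisons are distorted against or in favour of older or comorbid patients. The protocol contains no data showing that such patients stop more often; section 9.3.4.3 only plans to explore the difference. Nor is Gray's test plainly better here, since it mixes a factor's effect on stopping with its effect on response.
- **The large figure is a worst case.** It is. The 11.4 points come from the slow-response case with every loss counted as a TDF stop, whereas section 9.1.2 combines stopping with loss to follow-up. Only stops before first CVR matter.
- **Little depends on it.** The protocol says "No formal hypotheses will be tested, as this will be a descriptive study", the sample size does not rest on time to CVR, and the share with CVR is estimated separately. This limits the severity. It does not remove the point, because the windowed proportions estimate a different quantity.

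**Conclusion.** The point holds as a matter of interpretation and display. Kaplan-Meier with stops censored is a legitimate estimate of response if nobody stopped, provided stopping is unrelated to response; the protocol's own list of reasons makes that proviso doubtful. It is not an estimate of the share of treated patients who reach CVR in practice, and should not be read as one.

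The size is about 1 to 5 points at week 144 if 8.75% to 17.5% of patients stop, depending on how fast response comes, and 5 to 11 points if the whole 35% is stopping. This rests on constant independent hazards, an assumed split of the 35%, borrowed response speeds, and the inference that stops are censored. A change is worth making but is not critical: no formal test or sample-size figure is affected.

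**What to change.** In section 9.3.4.2:

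- Add a cumulative-incidence (Aalen-Johansen) curve of CVR, with TDF discontinuation of at least 28 days and death as competing events. Use it for any statement about the share of treated patients who reach CVR.
- Censor that curve only for loss to follow-up, consent withdrawal, other administrative withdrawal and end of study.
- Keep the Kaplan-Meier curve, labelled as assuming that no one stops TDF.
- Keep log-rank and Cox for predictors, labelled as cause-specific.

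The cost is a few lines of wording and one additional procedure. Treatment duration and reasons for stopping are already collected under sections 7.3 and 8.2, so no new data are needed. The downside is that the reported cumulative response will be somewhat lower than 1-KM.
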